8.2.4 Clinical laboratory tests

See the SoA footnotes (Section 1.3) for the list of clinical laboratory tests to be performed at the times given in the SoA. Clinical laboratory tests will be performed at a local

Clinical Trial Protocol Trial number: BNT165-01 Page 44 of 82 Version: 4.0 Date: 13 FEB 2023

laboratory. For details of all assessed blood clinical laboratory parameters, see Section 10.3.

All protocol-required clinical laboratory tests must be conducted in accordance with the local laboratory standard. The investigator must review the laboratory report, and document this review with their signature and date of signature.

All laboratory tests with values considered clinically significantly abnormal during participation in the trial should be repeated until the values return to normal or baseline or are no longer considered clinically significant by the investigator or trial Medical Monitor. If such values do not return to normal/baseline within a period of time judged reasonable by the investigator, the etiology should be identified, and the sponsor notified.

If laboratory values from non-protocol-specified laboratory assessments performed at the laboratory require a change in trial subject management or are considered clinically significant by the investigator (e.g., SAE, AE), then the results must be recorded in the CRF.

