8.5.1 Myopericarditis

Any subject who reports acute chest pain, shortness of breath, palpitations, or any other symptom(s) that might be indicative of myocarditis or pericarditis within 6 weeks after an IMP dose must be specifically evaluated by a cardiologist for possible myocarditis or pericarditis.

The same applies for any subject in whom a new ECG abnormality (compared to baseline) consistent with probable or possible myocarditis or pericarditis or abnormal Troponin I level is observed within 6 weeks after each IMP dose administration. In addition to a clinical evaluation, the following should be performed:

ECG and

Clinical Trial Protocol Trial number: BNT165-01 Page 52 of 82 Version: 4.0 Date: 13 FEB 2023

 Measurement of the Troponin I level, if not already obtained (for cases where the abnormal Troponin I level is the initial reason for evaluation).

If myocarditis or pericarditis is suspected based upon the initial evaluation, the following should also be performed:

- Cardiac echocardiogram and/or
- Cardiac magnetic resonance study

Any case of myocarditis, pericarditis or myopericarditis, that is assessed as possibly related by the investigator will constitute a trial treatment pausing rule per Section 7.1.1, until the IRC reviews the event. The ECG abnormalities consistent with probable or possible myocarditis or pericarditis are those judged as such by a cardiologist, including:

- Sustained atrial or ventricular arrhythmias
- Second-degree Mobitz Type II or worse atrioventricular block, new bundle branch block
- Diffuse ST-segment elevation or PR-segment inversion, compatible with pericarditis

The investigators must followup on any case of clinically significant ECG abnormality with troponins and other relevant tests till resolution. If there are such abnormal tests after the first dose, then investigators must make all relevant assessments before the second dose in reasonable time.

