8 STATISTICAL ANALYSES

8.1 General considerations

In general, all summaries will be displayed by individual vaccine DL and combined placebo. A total group, combining all subjects on placebo and active vaccine, will be presented in addition for accounting (subject disposition), demographics and other baseline characteristics and protocol deviations as applicable unless otherwise specified.

No formal statistical comparisons between vaccine DL of BNT165b1 and placebo will be performed. Missing data, other than that described for partial or missing dates for AEs/concomitant medications/vaccinations (as described below) will not be imputed.

Continuous variables will be summarized using the following descriptive statistics: number of subjects with non-missing data (n), mean, SD, median, minimum (min) and maximum (max).

Categorical variables will be summarized by absolute and relative frequencies (n and %) of subjects in each category and the number of subjects with missing data ('missing' category will be presented if there is one or more missing value).

For event-driven occurrence data (e.g., adverse event, concomitant medication, etc.) percentages will be based on the number of subjects in the analysis set (N). For reported visit data (e.g., lab etc.) percentages will be based on the number of subjects with non-missing values (n).

The rates of binary endpoints such as safety variables (systemic and local reactions) will be provided.

Page 13 of 36 Version: 3.0 Date: 08 MAY 2024

All data collected during the trial will be listed based on safety set unless otherwise specified. The trial day will be presented as appropriate. Listings will be sorted by dose level, site number, subject number, and date of assessment or date of onset (if applicable).

All trial data will be presented at the visit as assigned in the Case Report Form (CRF). No windowing of data for the purposes of assigning to a visit will occur. Unscheduled assessments will not be included in summaries/analysis but will be included in the listings.

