8.5.5 Laboratory assessments

Hematology, clinical chemistry, urinalysis, Follicle stimulating hormone (FSH) and pregnancy tests will be performed by a local laboratory.

For the purposes of summarizing and presentation in tables and listings, all laboratory values will be presented in System International (SI) units. If a laboratory value is reported

Statistical Analysis Plan (SAP) BNT165-01

BioNTech SE Confidential Page 25 of 36 Version: 3.0 Date: 08 MAY 2024

using a nonnumeric qualifier e.g., less than (<) a certain value, or greater than (>) a certain value, the given numeric value will be used in the summary statistics, ignoring the nonnumeric qualifier.

Absolute values of clinical laboratory variables at each protocol scheduled visit and its change from baseline will be summarized using descriptive summary statistics for each parameter listed in the protocol.

Categorical variables will be summarized using number and percentage.

Shift tables from baseline to each visit will be presented. Shifts will be done based upon grading from FDA guidance for industry 'Toxicity Grading Scale for Healthy Adult and Adolescent Volunteers Enrolled in Preventive Vaccine Clinical trials'.

Abnormal and clinically significant, abnormal and not clinically significant and normal laboratory values will be summarized for each parameter by visit.

All laboratory data will be presented in the data listings and abnormal clinical laboratory values will be flagged in the listing. Laboratory values that are below or above the normal reference ranges will be flagged.

The results of FSH, pregnancy test and Urinalysis (Dipstick and Microscopy tests) results will be listed only.

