8.5.6 Vital signs

Vital sign parameters to be summarized include systolic and diastolic blood pressure, heart rate, respiratory rate and oral body temperature. Body temperature will be presented in Celsius (°C).

Absolute values for vital sign parameters at each visit and change from baseline to each post-baseline visit will be summarized using descriptive summary statistics for each parameter. Note that vital signs will be collected both pre- and post-IMP administration.

Abnormal clinically significant, abnormal not clinically significant, and normal values of will be listed only.

8.5.7 12-Lead electrocardiogram (ECG)

Absolute values of heart rate collected at each time-point, and its change from baseline to each post-baseline time-point will be summarized using descriptive summary statistics for the subjects in safety set.

In addition, the investigators evaluation at each visit (Normal, Abnormal – not clinically significant and Abnormal – clinically significant) will be tabulated by visit.

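### Unscheduled laboratory and ECG results go to listings only and no worst post-baseline summary is planned, so the dose-level tables can show a milder result than the trial recorded

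*SAP*

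**What the plan says.** The rule is general. SAP 8.1 says: "Unscheduled assessments will not be included in summaries/analysis but will be included in the listings". The later sections do not override it.

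- **Laboratory (SAP 8.5.5):** "Absolute values of clinical laboratory variables at each protocol scheduled visit and its change from baseline will be summarized using descriptive summary statistics". For toxicity grades: "Shift tables from baseline to each visit will be presented". The table of normal, abnormal and clinically significant results is also by visit.
- **ECG (SAP 8.5.7):** "Absolute values of heart rate collected at each time-point, and its change from baseline to each post-baseline time-point will be summarized". The investigator's three-level evaluation follows the same pattern: "Abnormal – not clinically significant and Abnormal – clinically significant) will be tabulated by visit".

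Neither section defines a worst value, or a shift to the worst grade, after dosing.

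The protocol creates results outside these visits. Section 8.2.4: "All laboratory tests with values considered clinically significantly abnormal during participation in the trial should be repeated". Section 8.5.1 requires a cardiac evaluation when suggestive symptoms, a new ECG abnormality or an abnormal troponin occur within 6 weeks of a dose. That evaluation includes an ECG and "Measurement of the Troponin I level, if not already obtained". Clinically significant ECG abnormalities must then be followed with troponin and other tests until they resolve.

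**The concern.** Unscheduled tests are done because a symptom or an abnormal result prompted them. Leaving them out of the tables is therefore an informative exclusion: the omitted values are more likely than the scheduled ones to be abnormal.

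Consider a subject whose scheduled 7 d result has a low grade and whose triggered test some days later has a higher one. The shift table places that subject at the lower grade, and the higher grade appears only in a listing. The same happens if a peak before day 7 has eased by the scheduled visit.

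This is a first-in-human dose-escalation trial whose primary objective is to describe safety for each dose level. A reader who compares dose levels from the laboratory and ECG tables could see a milder profile than the database holds.

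**Working it through.** The plan gives no figure on this point, so there is nothing to reproduce. The check has two parts: how much of the cardiac window the schedule covers, and which findings reach another table.

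**1. Schedule against the cardiac window**

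Inputs:
- Laboratory tests (the panel includes troponin) and 12-lead ECG fall at V1, V3, V5, V7, V9 and V10 after screening (schedule of activities). V1, V5 and V9 are pre-dose.
- Doses are on days 1, 57 and 183. The post-dose visits are at 7 d, window +2 d, so nominally days 1 + 7 = 8, 57 + 7 = 64 and 183 + 7 = 190.
- The cardiac window is 6 weeks: 6 × 7 = 42 d (protocol 8.5.1).

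| Dose | Scheduled post-dose test inside 42 d | Next scheduled test |
|---|---|---|
| 1 | 8 − 1 = day 7 | 57 − 1 = 56 d |
| 2 | 64 − 57 = day 7 | 183 − 57 = 126 d |
| 3 | 190 − 183 = day 7 | none; V10 to V14 is 365 − 7 = 358 d |

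Each window holds exactly one scheduled laboratory and ECG time point. The days left after it are:
- visit on day 7: 42 − 7 = 35 d, and 35/42 = 83%
- visit on day 9: 42 − 9 = 33 d, and 33/42 = 79%

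A triggered test on any of those days is unscheduled and so listing-only. The days before the visit have no scheduled test either, but the 7 d value then follows.

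**2. What the AE tables pick up**

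- Clinically significant laboratory and ECG abnormalities meet the AE definition whenever they are found (protocol 10.4.1.1).
- AEs and MAAEs are tabulated for onset up to 28 d after each dose, SAEs through Visit 14, and AEs leading to IMP discontinuation or study withdrawal whenever reported (SAP 8.5.4.1 and 8.5.4.2).
- The cardiac window outlasts the 28 d limit by 42 − 28 = 14 d, that is, days 29 to 42.
- If a laboratory abnormality is a sign of a disease, only the diagnosis is recorded as the AE. If it causes symptoms without a diagnosis, only the symptoms are (protocol 10.4.1.3.2).
- Findings documented as not clinically significant are not to be recorded as AEs (protocol 10.4.3).

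| Unscheduled finding | By-visit tables | AE tables |
|---|---|---|
| Clinically significant, onset to day 28 | no | yes, as an event |
| Its measured peak, and its laboratory grade where the AE is a diagnosis or symptom | no | no |
| Abnormal, not judged clinically significant | no | no |
| Non-serious, onset on days 29 to 42, no withdrawal from IMP or study | no | no |
| Serious, or leading to withdrawal | no | yes, as an event |

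All of these remain in the listings. The same abnormal laboratory value found at a scheduled visit would enter the by-visit clinical-significance table and, if gradable, the shift table.

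**The case against.** The case against is substantial, and most of its facts stand.

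- A reader might infer that the worst post-dose values, or the whole cardiac work-up, can reach no table. The documents do not support that. Troponin and ECG are scheduled about 7 d after every dose and tabulated, with minimum and maximum for laboratory values. A worst value found at a scheduled visit is shown.
- A reader might infer that serious cardiac findings would go unseen. They would not. Clinically significant findings become AEs, SAEs or MAAEs within the limits above. Possibly related myocarditis or pericarditis is also a criterion for permanent discontinuation (protocol 7.1.3), and AEs leading to discontinuation are tabulated without a day limit.
- Unscheduled values are not discarded. All are listed, and abnormal laboratory values are flagged. With 60 subjects and no formal comparisons, listings can be read subject by subject.
- The primary endpoints are solicited reactions, AEs, SAEs and MAAEs, and laboratory and ECG data are other safety data. Escalation rests on the review committee's look at all available data, not on these tables.
- Repeats after a scheduled clinically significant result will often document recovery from a value already tabulated.
- It is tempting to size the effect by the weight of one subject among the 16 vaccinated per cohort. That is only the weight of any one subject. The documents do not say how often an unscheduled value exceeds the scheduled one.

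These points shrink the concern to a reporting gap but do not close it. An event in an AE table does not carry the measured peak. An abnormality judged not clinically significant has no AE route. Listings do not give counts by dose level.

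**Conclusion.** The point holds as a limited reporting gap. SAP 8.1 sends unscheduled results to listings only, and no worst post-baseline summary offsets this. The laboratory shift, laboratory clinical-significance and ECG evaluation tables can therefore show a milder result than the worst one recorded.

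The gap has three parts: the measured peak and its laboratory grade; unscheduled abnormalities not judged clinically significant; and non-serious events with onset on days 29 to 42 that lead to no withdrawal from IMP or study.

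Its extent in time is 33 to 35 of 42 days after each dose. That is a count of calendar days on nominal visit days with the +2 d window. It is not a rate of missed abnormalities, and the number of affected subjects cannot be estimated from the documents. The conclusion also assumes that triggered tests are recorded as unscheduled, as the SAP's visit rule implies: data stay at the visit assigned in the CRF, without windowing.

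The primary AE and reactogenicity analyses and the escalation decisions are not affected.

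**What to change.** Keep the by-visit tables on scheduled values. Amend SAP 8.1, 8.5.5 and 8.5.7 to add a worst post-baseline column, overall and after each dose, to three tables: the laboratory grade shift, laboratory clinical-significance and ECG evaluation tables.

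Suggested text for SAP 8.1: *By-visit summaries use scheduled assessments only. Worst post-baseline summaries use all post-baseline assessments, scheduled and unscheduled, overall and after each dose.*

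Two details should be stated:
- **Worst:** the highest toxicity grade for the shift table, and the most serious of the three categories for the other two tables. Where the grading scale does not cover a parameter, the clinical-significance table carries it.
- **After each dose:** from that dose to the next, or to the end of follow-up after Dose 3. Pre-dose samples on a dosing day belong to the preceding interval. The date rule in SAP 8.1.1 alone would assign them to the new dose.

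The column tabulates the worst grade or category, including results from days 29 to 42. It does not extend the AE tables, and numeric peaks stay in the listings. The cost is a short SAP amendment and a little programming. No new data are needed, since the values are already planned for the listings.

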8.1.1 General definitions

Baseline is defined as last available value prior to first dose of trial IMP.

Generally, if there are multiple pre-baseline assessments available for a particular day, the assessment that is closest to the day (and time if collected) of the first dose of a trial treatment will be used as the baseline value.

Change from baseline: Unless otherwise specified, this will be calculated as follows:

Change from baseline = post-baseline assessment value – baseline assessment value.

If either the baseline or post-baseline assessment value is missing, the change from baseline is set to missing as well.

Body mass index (BMI) will be calculated as follows:

BMI
$$\left(\frac{\text{kg}}{\text{m}^2}\right) = \frac{\text{Weight (kg)}}{\text{Height(m)}^2}$$

Temperatures collected in °F will be converted to °C as follows:

$$^{\circ}C = (^{\circ}F - 32) * 5/9$$

Duration will be calculated as follows:

• Duration = last observation date - first observation date + 1.

For conversion of days to months or years the following rules will be applied:

- 1 month = 30.4375 days
- 1 year = 365.25 days

Trial Day will be calculated as follows:

- If assessment/onset date < date of first IMP dose, then trial day = assessment date
 date of first IMP dose
- If assessment/onset date >= date of first IMP dose, then trial day = assessment/onset date - date of first IMP dose + 1

That is, trial day 1 indicates the date of first IMP dose.

The day relative to dose 2 or dose 3 will be calculated as follows:

Statistical Analysis Plan (SAP)

BNT165-01

Page 14 of 36

Version: 3.0

Date: 08 MAY 2024

 If assessment/onset >= date of second IMP dose and < date of third IMP dose, then day relative to dose 2 = assessment/onset date - date of second IMP dose + 1

If assessment/onset >= date of third IMP dose, then
 day relative to dose 3 = assessment/onset date – date of third IMP dose + 1

All trial data will be presented at the visit in the visit assigned in the Case Report Form (CRF)/visit assigned in external data. No windowing of data for the purposes of assigning to a visit will occur.

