- c Vital signs: systolic/diastolic blood pressure, pulse rate, respiratory rate, and oral body temperature.
- d Viral screen: screen for HIV 1, HIV 2, Hepatitis B, and Hepatitis C.
- e Clinical laboratory tests: (Chemistry) alkaline phosphatase, alanine transaminase, creatinine, c-reactive protein, albumin, amylase, aspartate transaminase, gamma glutamyl transpeptidase, total bilirubin, blood urea nitrogen, glucose, lipase, sodium, potassium, calcium, troponin, IgG, IgM and IgA; (Hematology) hemoglobin, hematocrit, red blood cell count, white blood cell count and differential (neutrophils, lymphocytes, monocytes, eosinophils, basophils), platelet count. Only in women who are not VOCBP (to confirm postmenopausal status): follicle stimulating hormone at Visit 0. Only for VOCBP: serum β-HCG at Visit 0.
- f On days with dosing, blood draws should be done pre-dose.
- g VOCBP: The serum β-HCG pregnancy test at Visit 0 is performed using the sample collected for clinical laboratory tests. Before each dosing, urine pregnancy tests will be performed using a commercial kit at the site and the trial subjects will be counseled about the need for consistent and correct use a highly effective method of contraception.
- h If justified by the collected data, the listed blood draw days and the draw volumes may be adapted if not increasing the total number of draw days or the total volume drawn. Leftover blood after completion of the immunogenicity assessments may be used for additional biomarker analyses.
- i Trial site personnel will remind the subjects to record the oral body temperature and the worst grade for each symptom in the e-diary at approximately the same time every evening on the day of IMP administration and then every day in the evening for a total of seven consecutive days. Ask/remind the subject to contact the site if they experience any severe or potentially life-threatening reactogenicity events.
- The AEs and MAAEs will be collected continuously until 28 d after each dose, and SAEs need to be recorded continuously until Visit 14.
- k Trial subjects will be contacted by phone for non-leading wellbeing calls at 5 h, 24±4 h (after Dose 3 only), and 48±4 h after each IMP dose.
- I Local reactogenicity assessed by the investigator pre-dose and up to 1 h after dosing.
- m 12-lead ECG will be performed pre-dose.
- n Subjects will make their last entries in the evening before the 7 d follow-up visit.

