6.4 Trial treatment compliance

Trial subjects will receive trial treatment directly from the investigator or a designee under medical supervision. The date and time of each dose administered must be recorded in the source documents and in the CRF. The dose of trial treatment and subject identification number will be confirmed at the time of dosing by a member of the trial site personnel other than the person administering the trial treatment.

See Section 8.4 for guidance on the treatment of overdose or errors in drug administration.

Page 37 of 82 Version: 4.0 Date: 13 FEB 2023

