8.3.1 Time period and frequency for collecting AE and SAE information

All AE and SAE information will be collected at the time points specified in the SoA (Section 1.3).

Non-serious AEs will only be collected as of first IMP dose administered while SAEs need to be recorded upon awareness starting once informed consent is given.

Adverse events and medically attended adverse events will be collected until 28 d after each dose and SAEs need to be recorded continuously until Visit 14 (52 weeks post-Dose 3).

Medical occurrences that begin after obtaining informed consent but before the start of trial treatment administration must be recorded on the respective Medical History/Current Medical Conditions section of the CRF and not in the section of the AE unless they qualify as SAEs.

Medical occurrences meeting the criteria for an SAE (see Section 10.4.2) must be reported as SAEs (see Section 8.3.4).

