10.4.3 Recording and follow-up of AEs and/or SAEs

AE and SAE recording

The investigator needs to assess and document any AE regardless of association with the use of the trial treatment during the period of observation (see Section 8.3.1).

- Data pertaining to AEs will be collected during each trial visit. Based on the trial subject's spontaneous description or investigator's inquiry or discovered in the course of examinations done during the visit, clinical significance of any sign or symptom needs to be evaluated by the investigator.
- Clinically significant findings need to be documented as AEs in the source data and CRF. Findings that are evaluated and documented in the source data as not clinically significant (e.g., an abnormal laboratory value without any clinical manifestation), should not be documented as AE.
- The investigator will then record all relevant AE information in the CRF and perform an assessment on:
 - Severity (see the section Assessment of severity)
 - Seriousness
 - Outcome
 - Causal relationship of the AE to the trial treatment/trial procedure
 - Any trial treatment action and/or any other action taken
 - All assessments as well as AE term (diagnosis/description), start date and time of onset, end date and time need to be documented in the CRF.
 - There may be instances when copies of medical records for certain cases are requested by the sponsor. In this case, all trial subject identifiers, with the exception of the subject number, will be redacted on the copies of the medical records before submission to the sponsor.
 - To avoid colloquial expressions, the AE should be reported in standard medical terminology. The investigator will attempt to establish a diagnosis of the event based on signs, symptoms, and/or other clinical information. Whenever possible, the diagnosis (not the individual signs/symptoms) will be documented as the AE. If a definitive diagnosis is not possible, the individual signs and symptoms should be recorded.

Assessment of severity

The assessment of AE and/or SAE intensity should be done consistently for all trial subjects treated with the same treatment and dose. In case of doubt, the trial Medical Monitor should be consulted.

The intensity of (serious) AEs will be graded by the investigator. For further guidance refer to the US FDA "Toxicity Grading Scale for Healthy Adult and Adolescent Volunteers

Clinical Trial Protocol Trial number: BNT165-01 Page 71 of 82 Version: 4.0 Date: 13 FEB 2023

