8.5.4.1 Overall summary of adverse events

The number and percentage of subjects reporting the below events will be summarized for the subjects in safety set.

- Unsolicited AEs with onset from Day1 through Day 28 post IMP dose will be summarized for each dose (i.e., 1st dose, 2nd dose, 3rd dose) and regardless of the number of doses received. All events entered on the "Adverse Events" eCRF page with an onset date within the above-mentioned timeframe will be analysed. This includes solicited events that persisted beyond Day 7 after IMP administration or that qualified as an SAE. The following will be analysed:
 - Any unsolicited AEs
 - Related AEs
 - AE of grade >=3
 - Related AEs of grade >=3
 - Any solicited reactogenicity event that continues longer than 7 d post-IMP administration or is an SAE
 - Unsolicited AEs leading to withdrawal of IMP
 - Unsolicited AEs leading to study withdrawal
 - SAEs, with onset from Day 1 through Visit 14. The following will be analysed:
 - Any SAEs
 - Related SAEs
 - SAEs of grade >=3
 - Related SAEs of grade >=3
 - MAAE, with onset from Day1 through 28 days after each dose. The following will be analysed:
 - Any MAAEs
 - Related MAAEs

Page 24 of 36 Version: 3.0 Date: 08 MAY 2024

- MAAEs of grade >=3
- Related MAAEs of grade >=3

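### After Doses 2 and 3 the SAP places AEs by calendar date alone, so an AE that starts on the dosing day before the injection is counted as post-dose

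*SAP*

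**What the plan says.** SAP 8.1.1 gives the condition for Dose 2 as "If assessment/onset >= date of second IMP dose and < date of third IMP dose" and the formula as "day relative to dose 2 = assessment/onset date - date of second IMP dose + 1". Dose 3 follows the same pattern, opening with "If assessment/onset >= date of third IMP dose, then". No clock time enters either rule.

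SAP 8.5.4.1 then states: "Unsolicited AEs with onset from Day1 through Day 28 post IMP dose will be summarized for each dose". It takes every record on the AE page of the eCRF whose onset date lies in that window. MAAEs use the same 28-day span after each dose. The matching primary estimands (Protocol Section 3, SAP 3.1) are the proportions of subjects with at least one AE, or at least one MAAE, up to 28 days after each dose.

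Before Dose 1 there is a safeguard. Protocol 8.3.1 sends "Medical occurrences that begin after obtaining informed consent but before the start of trial treatment administration" to the medical history section unless they are serious, and SAP 8.5.4 limits unsolicited AEs to those that start after the first IMP administration. Neither document has a matching rule for Dose 2 or Dose 3.

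The times needed are recorded. Protocol 6.4: "The date and time of each dose administered must be recorded in the source documents and in the CRF". Protocol 10.4.3, for AEs: "start date and time of onset, end date and time need to be documented in the CRF".

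**The concern.** Trial procedures precede the injection on each dosing day. Footnote f of the schedule of activities says "On days with dosing, blood draws should be done pre-dose", and the ECG and one set of vital signs are also pre-dose. The volume row shows 150 mL at Visit 5 (Dose 2) and 155 mL at Visit 9 (Dose 3). Protocol 10.4.3 gives discomfort after a blood draw as an example of a procedure-related event and requires such events on the AE page, which is the page that SAP 8.5.4.1 counts. The schedule also has AEs recorded at Visits 5 and 9.

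An event that precedes an injection cannot be an event after it, yet the date rule makes it one. What is at stake is the accuracy of a primary descriptive result: the per-dose AE and MAAE proportions for Doses 2 and 3, in groups small enough for one subject to show.

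**Working it through.** The plan states no figure for this point, so there is none to reproduce. The check applies the SAP rule to a test case and then sizes one misplaced event.

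**Inputs**
- Dosing days 1, 57 and 183 (Protocol 6.1). Visit windows are ±2 days for Dose 2 and ±7 days for Dose 3 (Protocol 1.3).
- Relative day = onset date − dose date + 1 (SAP 8.1.1). Per-dose window Day 1 to 28 (SAP 8.5.4.1).
- 16 vaccine and 4 placebo subjects per cohort (Protocol 4.1.1). Placebo is combined across three cohorts (SAP 8.1), so 3 × 4 = 12.
- AE percentages use the number of subjects in the analysis set as denominator (SAP 8.1), taken here as the full planned group.

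**Step 1: the date rule.** Take an AE at 09:00 and an injection at 10:30 on the same day.
- Day 57: 57 − 57 + 1 = Day 1 relative to Dose 2, so it is counted.
- Day 183: 183 − 183 + 1 = Day 1 relative to Dose 3, so it is counted.

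**Step 2: the same events placed by date and time.** Each now belongs to the interval after the previous dose.
- Before Dose 2: Day 57 relative to Dose 1 (Day 55 to 59 within the visit window).
- Before Dose 3: 183 − 57 + 1 = Day 127 relative to Dose 2. With the visit windows the range is 176 − 59 + 1 = 118 to 190 − 55 + 1 = 136.

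Both lie outside Day 1 to 28. These events therefore belong to no post-dose window, and they also enter the summary taken regardless of the number of doses only because of the date rule.

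**Step 3: effect of one event.** The statistic is a proportion of subjects with at least one AE, so it moves only if the subject has no other AE in that 28-day window.
- Vaccine dose group: 1/16 = 6.25 percentage points.
- Combined placebo: 1/12 = 8.3 percentage points.

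**Step 4: how often.** The documents give no rate. Assume that a share p of dosing visits has a recorded AE starting before the injection, with p from 1% to 3%. Per dose column of 16, the expected number is 16p and the chance of at least one is 1 − (1 − p)^16.

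| p | Expected events | Chance of at least one |
|---|---|---|
| 1% | 0.16 | 15% |
| 2% | 0.32 | 28% |
| 3% | 0.48 | 39% |

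**The case against.** The strongest reply is that such events may not be collected. AEs and MAAEs are to be collected until 28 days after each dose, and a pre-injection event on Day 57 or Day 183 comes long after that. This has force, but the documents pull both ways: AEs are recorded at Visits 5 and 9, procedure-related events must go on the AE page, and SAP 8.5.4.1 analyses whatever is entered with a date in the window.

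Other points shrink the effect, and they stand:
- Protocol 10.4.3 has procedure-related events labelled as such and kept apart from events caused by the IMP. The rows for related AEs should be largely spared.
- Febrile or other acute illness within 48 hours before a dose is a reason for deferral (Protocol 7.1.2), which removes many same-day illnesses.
- Counting the whole dosing day as post-dose over-reports AEs rather than hiding them, the safer direction in a first-in-human trial.

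A reader might infer that later-dose AE rates are inflated as a matter of fact, or that the contrast between doses or between vaccine and placebo is biased. The documents do not support this. They give no rate for such events. Vaccine and placebo subjects at every dose level share the same pre-dose procedures. No hypotheses are tested, and no formal comparison of vaccine with placebo is made (SAP 4 and 8.1). Nor does a contrast of Dose 1 with later doses appear as a planned inference. Pooling Visits 5 and 9 (32 visits per dose level) would raise the chance of at least one event to 28-62% under the same assumption, but the estimand is per dose, so a single column of 16 is the right unit. Finally, an AE that starts on an earlier date is not pulled in; only the dosing date itself is affected.

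**Conclusion.** The point holds as a small defect in the rule. As written, the SAP counts a recorded AE or MAAE that starts on the day of Dose 2 or Dose 3 before the injection as Day 1 after that dose, whereas non-serious events of this kind before Dose 1 are excluded. The consequence is a possible slight over-count in the all-causality rows for Doses 2 and 3. SAEs are summarised from Day 1 through Visit 14 rather than by 28-day dose window, so those rows do not depend on this rule at Doses 2 and 3.

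The shifts of 6.25 and 8.3 points apply per affected subject with no other AE in the window, at the planned group sizes. The expected count of 0.16-0.48 and the 15-39% chance per dose column rest wholly on the assumed 1-3% rate and on such events reaching the AE page. Few are likely. The case for acting is that the affected figures are primary descriptive results and the times needed to classify the events correctly are already required in the CRF.

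**What to change.** In SAP 8.1.1 and 8.5.4, add a rule for AEs and MAAEs dated on the day of Dose 2 or Dose 3:
- Compare the recorded onset time with the recorded injection time.
- If onset is before the injection, do not count the event as post-dose for that injection. Show it in a separate line, such as pre-injection on dosing day, and keep it in the listings. State that it also falls outside the Day 1 to 28 window of the previous dose, so that its absence from the per-dose table is explicit.
- If the onset time is missing, count the event as post-dose.

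The SAP already works this way elsewhere: 8.1.1 uses time, where collected, to choose among multiple pre-baseline assessments on a day, and 8.5.2.2 summarises local reactions before and after the injection separately. The cost is a short addition to the SAP and a few lines of code, with no new data and no change to trial conduct. The downside is that a few events with missing or uncertain onset time will still follow the conservative default.
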